6.1. Demographic and Other Baseline Characteristics

Demographic and baseline characteristics, concomitant medications and administrative status for study drug will be summarized with descriptive statistics. Continuous variables will be summarized with n, mean, SD, median, minimum and maximum. Categorical variables will be summarized with frequency (number of subjects and/or number of events) and percentage.

6.1.1. Demographic and Baseline Characteristics

- 1) Sex will be presented in frequency and percentage.
- 2) Age (year) will be presented in n, mean, SD, median, minimum and maximum, and frequency and percentage of categorized age groups.

$$Age \text{ (year)} = \frac{(Start \text{ date of first administration}) - (Date of birth)}{365.25}$$

- 3) Pediatric subjects will be presented in frequency and percentage.
- 4) Geriatric subjects will be presented in frequency and percentage.
- 5) Classification (inpatient/outpatient status) will be presented in frequency and percentage.
- 6) Height (cm) will be presented in n, mean, SD, median, minimum and maximum.
- 7) Weight (kg) will be presented in n, mean, SD, median, minimum and maximum.

Statistical Analysis Plan for rPMS

6.1.2. Diagnosis of advanced renal cell carcinoma (aRCC)

- 1) Duration of aRCC (month) will be presented in n, mean, SD, median, minimum and maximum. Also, frequency and percentage of each group categorized according to the distribution of duration of aRCC will be presented.

Duration of aRCC (month)

$$= \frac{(Start\ date\ of\ first\ administration) - (Date\ of\ initial\ diagnosis) + 1}{30.4375}$$

- 2) Cell component of aRCC will be presented in frequency and percentage.
- 3) Metastasis will be presented in frequency and percentage. In case of 'yes', categorized metastasis site will be presented in frequency and percentage.
- 4) Primary lesion surgery will be presented in frequency and percentage.

6.1.3. Medical History

- 1) Medical history
 - Medical history will be presented in frequency and percentage.
 - Medical history classified by System Organ Class (SOC) and Preferred Term (PT) according to the latest version of Medical Dictionary for Regulatory Activities (MedDRA) in detail will be presented in each frequency and percentage.
 - Renal impairment will be presented in frequency and percentage.
 - Hepatic impairment will be presented in frequency and percentage.
- 2) Allergic history will be presented in frequency and percentage.

6.1.4. Prior Chemotherapy/Immunotherapy and Radiation Therapy

- 1) Prior chemotherapy/immunotherapy
 - Prior chemotherapy will be presented in frequency and percentage.
 - Prior chemotherapy classified by Level 1 and Level 2 according to the latest version of Anatomical Therapeutic Chemical (ATC) classification system in detail will be presented in each frequency and percentage.
 - Prior immunotherapy will be presented in frequency and percentage.
 - Prior immunotherapy classified by Level 1 and Level 2 according to the latest version of ATC classification system in detail will be presented in each frequency and percentage.
- 2) Prior radiation therapy will be presented in frequency and percentage.

6.1.5. Concomitant Medication

- 1) Concomitant medication will be presented in frequency and percentage.

Statistical Analysis Plan for rPMS

- 2) Concomitant medication classified by Level 1 and Level 2 according to the latest version of ATC classification system in detail will be presented in each frequency and percentage.

6.1.6. Administrative Status for INLYTA®

- 1) Period of first administration* will be presented in frequency and percentage.

*Sub-group 1: Subjects who are first administered INLYTA® during the study period

Sub-group 2: Subjects who has continued administration of INLYTA® since the time prior to the contract date

- 2) Duration of administration (day) will be presented in n, mean, SD, median, minimum and maximum. Also, frequency and percentage of each group categorized according to the distribution of duration of administration will be presented.

$$\text{Duration of administration (day)} = \sum_{\text{First}}^{\text{Last}} \{(\text{End date}) - (\text{Start date}) + 1\}$$

- 3) Total dose (mg) will be presented in n, mean, SD, median, minimum and maximum.

$$\text{Total dose (mg)} = \sum_{\text{First}}^{\text{Last}} \{ (\text{Single dose} \times \text{Daily dosing frequency}) \} \\ \times \{ (\text{End date}) - (\text{Start date}) + 1 \}$$

- 4) Daily average dose (mg/day) will be presented in n, mean, SD, median, minimum and maximum. Also, frequency and percentage of each group categorized according to the distribution of duration of daily average dose will be presented.

$$\text{Daily average dose (mg/day)} = \frac{\text{Total dose}}{\text{Duration of administration}}$$

6.2. Safety Analyses

Safety analyses will be performed based on data of safety analysis set. All adverse events in CRF will be classified by System Organ Class (SOC) and Preferred Term (PT) according to the latest version of Medical Dictionary for Regulatory Activities (MedDRA).

- 1) All adverse events investigated after administration of INLYTA® will be summarized with the number of subjects having adverse events, incidence of adverse events with 95% confidence interval (CI) and the number of adverse events by categorizing as follows.
 - Serious adverse events and serious adverse drug reactions
 - Unexpected serious adverse events and unexpected serious adverse drug reactions
 - Unexpected adverse events and unexpected adverse drug reactions
 - Adverse events and adverse drug reactions
- 2) All adverse events investigated after administration of INLYTA® will be summarized with the frequency and percentage of adverse events by categorizing as follows.

Statistical Analysis Plan for rPMS

- Occurrence status of adverse events by their severity
 - Grade 1 (Mild)
 - Grade 2 (Moderate)
 - Grade 3 (Severe or medically significant)
 - Grade 4 (Life-threatening consequences)
 - Grade 5 (Death related to AE)
- Occurrence status of adverse events by their outcome
 - Recovered
 - Recovered with sequelae
 - Recovering
 - Not recovered
 - Unknown
- Occurrence status of adverse events by their seriousness
 - SAE
 - Results in death
 - Is life-threatening
 - Requires inpatient hospitalization or prolongation of hospitalization
 - Results in persistent or significant disability/incapacity (substantial disruption of the ability to conduct normal life functions)
 - Results in congenital anomaly/birth defect
 - Other important medical event: if it is determined that the event may jeopardize the subject or may require intervention to prevent one of the other outcomes listed in the definition above
 - Non-SAE
- Occurrence status of adverse events by their causality to INLYTA®
 - Related to INLYTA®: ① Certain
 - ② Probable/likely
 - ③ Possible
 - ⑤ Conditional/unclassified
 - ⑥ Unaccessible/unclassifiable
 - ⑦ Not applicable
 - Not related to INLYTA®: ④ Unlikely
- Occurrence status of adverse events by their other causality (In case of 'not related to INLYTA®')
 - Disease under the study
 - Other diseases
 - Concomitant treatment drug or non-drug

Statistical Analysis Plan for rPMS

- Others
- Occurrence status of adverse events by action
 - Discontinuation (permanently, temporarily or delayed)
 - Dosage reduced
 - Dosage increased
 - No change
 - Unknown
 - Not applicable
- 3) Occurrence status of adverse events by demographic and other baseline characteristics
 - The incidence of adverse events and 95% CI will be presented by categorical variables of demographic and other baseline characteristics.
 - To identify statistically significant difference in incidence of adverse events by categorical variables of demographic and other baseline characteristics, Chi-square test (χ^2 test) or Fisher's exact test (if the expected frequency for each cell under 5 is more than 20%) will be performed.
- 4) Analysis of factors that affect the safety
 - In the re-examination report, logistic regression or multivariate analysis will be performed and an odds ratio with 95% CI and p-value will be presented to identify the factors that affect incidence of adverse events in demographic and other baseline characteristics.
- 5) Analysis for special patient populations [pediatric subjects (aged < 19 years), geriatric subjects (aged \geq 65 years), subjects with renal impairment, subjects with hepatic impairment]
 - Adverse events and adverse drug reactions collected in each special patient population will be presented the number of subjects having adverse events, incidence of adverse events and the number of adverse events for each SOC and PT.
- 6) Analysis for population except from safety analysis
 - Adverse events and adverse drug reactions collected in population except from safety analysis will be presented the number of subjects having adverse events, incidence of adverse events and the number of adverse events for each SOC and PT.

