## **3. RESEARCH METHODS**

### **3.1. Study design**

Observational, non-interventional drug and multi-center study in which subjects will be administered as part of routine practice at Korean health care centers by accredited physicians. At least 3000 subjects should be enrolled in this study based on the Article 6 of “Basic Standards for the Re-examination of New Medicines” notified by MFDS. However, with additional 3 years of study period, at least 100 subjects who are being treated with Inlyta within the approved indication will be studied for total of 9 years according to the review result by the MFDS per Pfizer’s request to adjust the number of subjects. The study can be performed in Korean health care centers where INLYTA® is prescribed for advanced renal cell carcinoma (aRCC) after failure of one prior systemic therapy which is the indication for INLYTA® and where post-marketing study is allowed by institutions.

To achieve the target sample size, the study is being conducted in prospective study design and retrospective study design.

Patients to whom INLYTA® is first administered or patients who are already on INLYTA® during the study period should be enrolled in the study. Observation should be done from treatment initiation of INLYTA® for at least 28 calendar days. There are no visits or activities mandated by this study and routine observation will be done during INLYTA® treatment.

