### **3.5. Study procedures**

#### **3.5.1. Study Duration**

As specified in the product license given by MFDS, this study was to be conducted for 6 years from the approval date of 22 Aug 2012 to 21 Aug 2018. On May 2018, MFDS has granted 3 additional years for the study, for total of 9 years for the study period.

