### 3.5.4.9. Safety

#### 3.5.4.9.1. Adverse Event

Every observed and reported adverse event, regardless of the causal relationship with the study drug, must be recorded on an adverse event section in case report forms. The query pattern of experience of adverse event to the subjects is as follow;

Patients who are prescribed with INLYTA® for the first time during the study period: “Have you had any health problem since last visit?”

Patients who are already on INLYTA® at the time of enrollment: all safety information will be collected from medical chart since the date of treatment initiation.

For adverse events repeating before and after administrating the study drug, record the date adverse event was first experienced and the date adverse event resolved. Background information on INLYTA® can be obtained from the current version of the local product document, which is the single reference safety document (SRSD) for information relating to INLYTA®.

Check either ‘yes’ or ‘no’ in adverse event section. If ‘yes’, record in detail.

- Adverse events: Record the name of adverse event. If possible, specify diagnosis, not individual symptoms. Record the name according to National Cancer Institute Common Terminology Criteria for Adverse Events (CTCAE) Version 5.0.
- Date of onset: Record the date of onset. Record approximate date if an actual date is unknown.
- Date of resolution: Record the date of resolution. Record approximate date if an actual date is unknown.
- Severity: Severity evaluation of adverse event must be done according to the NCI CTC grade.
  - The physician will use the following definitions of severity in accordance with the National Cancer Institute Common Terminology Criteria for Adverse Events (CTCAE) Version 5.0 to describe the maximum intensity of the adverse event:

Grade	Definition
Grade 1	Mild; asymptomatic or mild symptoms; clinical or diagnostic observations only; intervention not indicated.
Grade 2	Moderate; minimal, local or noninvasive intervention indicated; limiting age-appropriate instrumental ADL*.
Grade 3	Severe or medically significant but not immediately life-threatening; hospitalization or prolongation of hospitalization indicated; disabling; limiting self care ADL**.
Grade 4	Life-threatening consequences; urgent intervention indicated.
Grade 5	Death related to AE.

Activities of Daily Living (ADL)

\*Instrumental ADL refer to preparing meals, shopping for groceries or clothes, using the telephone, managing money, etc.

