### **5.1.2. Reporting period**

For each patient, the safety event reporting period begins at the time of the patient's first dose of Inlyta or the time of the patient's informed consent if s/he is already exposed to Inlyta, and lasts through the end of the observation period of the study, which must include at least 28 calendar days following the last administration of a drug under study; a report must be submitted to Pfizer Safety (or its designated representative) for any of the types of safety events listed in the table above occurring during this period. If a patient was administered a drug under study on the last day of the observation period, then the reporting period should be extended for 28 calendar days following the end of observation. Most often, the date of informed consent is the same as the date of enrollment. In some situations, there may be a lag between the dates of informed consent and enrollment. In these instances, if a patient provides informed consent but is never enrolled in the study (e.g., patient changes his/her mind about participation, failed screening criteria), the reporting period ends on the date of the decision to not enroll the patient.

If the investigator becomes aware of a SAE occurring at any time after completion of the study and s/he considers the SAE to be related to Inlyta, the SAE also must be reported to Pfizer Safety.

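### Adverse event incidence is a crude proportion with no allowance for unequal observation time, so sub-group and factor differences may reflect length of exposure rather than risk

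*SAP*

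**What the plan says.** SAP 6.2 item 1 reports the number of subjects with AEs, "incidence of adverse events with 95% confidence interval (CI) and the number of adverse events". The shells carry this out as n(%) of subjects with an event count (Table 8), with a 95% CI added in Tables 9, 11, 13 and 15. Table 8 puts the two sub-groups in adjacent columns without a p-value.

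Item 3 applies chi-square or Fisher tests "To identify statistically significant difference in incidence of adverse events by categorical variables of demographic and other baseline characteristics" (Tables 23 and 24). Item 4 fits a logistic regression for AE yes/no (Table 25), with no covariate list, offset or time scale. Under SAP 5.1 tests are two-sided at 5%, and SAP 6.4 repeats these analyses within each sub-group.

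On length of observation:

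- Protocol 3.1: "Observation should be done from treatment initiation of INLYTA® for at least 28 calendar days". No maximum is given.
- Protocol 3.5.1: "MFDS has granted 3 additional years for the study, for total of 9 years for the study period".
- Protocol 5.1.2: the safety period runs to the end of observation, "which must include at least 28 calendar days following the last administration of a drug under study", so it follows each patient's own treatment duration.
- For patients already on the drug, Protocol 3.5.4.9.1 says "all safety information will be collected from medical chart since the date of treatment initiation", whereas Protocol 5.1.2 starts their reporting period at "informed consent if s/he is already exposed to Inlyta".

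SAP 6.1.6 summarises exposure on its own: "Duration of administration (day) will be presented in n, mean, SD, median, minimum and maximum". It is never a denominator for AEs, but duration of administration in categories is one of the factors tested in Table 24, under a title that classes it as a baseline characteristic.

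**The concern.** The proportion of subjects with at least one AE rises with time observed. If two groups have the same risk per month but one is observed longer, that group shows the higher incidence. Treatment duration differs between patients in routine practice. It is also likely to differ between the sub-groups by construction: Sub-group 2 consists of patients still on drug at the contract date (SAP 3.4), and those who finished before that date are excluded (SAP 3.1).

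Monitoring AEs is part of the stated objective. At stake is whether a difference in Table 8, or a significant factor in Tables 23 to 25, is read as a difference in risk when it may be a difference in follow-up.

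Duration of administration is a sharper case. Longer treatment gives more time for an AE to appear, while an AE can end treatment (discontinuation is one of the recorded actions). The two effects push the association in opposite directions, so its p-value cannot be read as evidence about a risk factor.

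**Working it through.** **Inputs from the documents.** Minimum observation is 28 days, which is 28/30.4375 = 0.92 months. The study period from 22 Aug 2012 to 21 Aug 2021 is 3,287 days, an outer bound for one individual and not a typical value. Tests are two-sided at 5%. The sample size is at least 100, a regulatory minimum with no power calculation behind it, so there is no plan figure to reproduce.

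**Assumptions, not in the documents.** A constant hazard h of first AE per month, equal in the groups compared; 50 v 50 subjects; the follow-up times shown.

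**Step 1. Crude incidence with identical risk,** p = 1 − exp(−h × t):

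| Time | h = 0.03 | h = 0.05 | h = 0.10 | h = 0.5 |
|---|---|---|---|---|
| 28 days | 2.7% | 4.5% | 8.8% | 36.9% |
| 6 months | 16.5% | 25.9% | 45.1% | 95.0% |
| 12 months | 30.2% | 45.1% | 69.9% | 99.8% |
| 24 months | 51.3% | 69.9% | 90.9% | 100.0% |

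At h = 0.05, 6 v 12 months gives 1 − exp(−0.3) = 25.9% against 1 − exp(−0.6) = 45.1%. The odds ratio is (0.451/0.549)/(0.259/0.741) = 2.35, with a true hazard ratio of 1. At h = 0.5 the outcome is nearly saturated and the absolute gap is under 5 percentage points.

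**Step 2. How often the planned test would reject.** Simulation of 4,000 runs, 50 v 50, exponential follow-up with a 28-day floor (means below are before the floor), identical hazards. The planned chi-square/Fisher rule is compared with an exact conditional test of first events per person-time:

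| Mean follow-up, months | Crude test, h = 0.03 / 0.10 / 0.5 | Person-time test, range |
|---|---|---|
| 6 v 6 | 5.4% / 4.6% / 4.4% | 3.9–4.2% |
| 6 v 12 | 27.2% / 39.8% / 23.6% | 3.8–4.7% |
| 3 v 12 | 69.1% / 89.8% / 75.7% | 3.5–4.5% |
| 6 v 24 | 85.5% / 92.1% / 62.1% | 3.2–4.8% |

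With equal mean follow-up the crude test holds its level. With unequal follow-up it rejects far more often than 5%, although risk is identical. The person-time test does well here because the simulation gives it the constant hazard it assumes.

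**Step 3. Is person-time alone enough?** Suppose instead that 60% of subjects have an AE at month 1 and nobody has one later. Crude incidence is 60% at any longer follow-up, which is correct. The first-event rate is 0.6/(0.6×1 + 0.4×6) = 0.6/3.0 = 0.20 per month with 6 months of follow-up, and 0.6/(0.6×1 + 0.4×24) = 0.6/10.2 = 0.059 with 24 months. A simple rate can therefore create the opposite artefact when AEs cluster early. A time-to-first-AE curve does not.

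**Step 4. Can time at risk be defined?** For already-treated patients, one protocol section collects AEs from treatment start and another begins reporting at consent. The two may be meant for different purposes (chart collection and reports to the sponsor), but the SAP does not say which defines the analysis window. If AEs count only from consent, time counted from first dose would include months in which no event could be recorded.

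**The case against.** A reader might infer that these comparisons mainly measure length of exposure. The documents do not support that. They give no follow-up distribution by sub-group or factor and no AE rates. A factor unrelated to treatment duration is not distorted, as the 6 v 6 row shows. If nearly every patient has some AE, or AEs come early, the effect on the any-AE proportion is small in absolute terms.

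A reader might also infer that every AE table has this defect, or that the two sub-groups are formally compared. Neither is so. Tables 16 to 22 count events, Tables 10, 12 and 14 are listings, and Table 8 carries no test. Analysing the sub-groups separately already keeps different exposure histories partly apart.

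Chi-square and Fisher tests are the protocol's own method (3.9.1.1), and Protocol 3.12 says the SAP follows a regulatory guideline that is not available here. Whether the crude tests could be dropped cannot be judged. Duration of administration could also enter the logistic model as a coarse adjustment.

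Most of this stands and limits the claim. It does not remove it. Serious AEs, unexpected AEs and individual preferred terms need not be near saturation. The SAP offers no way to tell which factors are unrelated to duration. A separate exposure summary adjusts nothing, and adjusting for a duration that AEs can shorten is not a sound repair.

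**Conclusion.** The concern holds in a limited form. The incidences in Tables 8, 9, 11, 13, 15 and 23 to 25 are not adjusted for unequal time at risk. Differences between sub-groups (descriptive), and between levels of any factor associated with treatment duration (tested at 5%), may reflect observation time. The Table 24 p-value for duration of administration is not interpretable as evidence of a risk factor.

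The size depends wholly on assumed hazards and follow-up. With equal risk and mean follow-up of 6 v 12 months, the planned test rejects in about 24–40% of runs instead of 5%, for hazards of 0.03 to 0.5 per month. With equal follow-up there is no distortion. The change is worth making, but the point does not invalidate the crude incidences as descriptions of what was observed.

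**What to change.** 1. State in the SAP when AE time at risk starts for already-treated patients, after reconciling Protocol 3.5.4.9.1 with 5.1.2, and when it ends. If AEs count only from consent, use delayed entry at consent.
2. Keep the crude n(%) and the chi-square/Fisher tests as the regulatory display.
3. Add, in total and for each sub-group, the cumulative incidence of first AE over time, or incidence in a fixed window from first dose, for any AE, serious AEs and the main preferred terms. Give events per person-year as a supplement only, because of step 3 above.
4. Base the interpretation of factors in Tables 23 to 25 on a time-to-first-AE comparison (log-rank or Cox).
5. Remove duration of administration from the Table 24 tests and from the candidates for the logistic model. Show it descriptively as exposure, by sub-group.
6. State as a limitation that Sub-group 2 is selected for having stayed on drug. No person-time method removes this.

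Cost: SAP wording and some programming. Drug start and stop dates and AE onset dates are already collected, and the SAP already plans Kaplan-Meier analyses for the efficacy endpoints. Approximate onset dates, which the protocol allows, will add some noise.

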Additionally, any suspected transmission via a Pfizer product of an infectious agent, pathogenic or non-pathogenic, is considered serious. The event may be suspected from clinical symptoms or laboratory findings indicating an infection in a subject exposed to a Pfizer product. The terms “suspected transmission” and “transmission” are considered synonymous. These cases are considered unexpected and handled as serious expedited cases by PV personnel. Such cases are also considered for reporting as product defects, if appropriate.

In case of serious adverse event, Drug Safety Unit in Pfizer Pharmaceuticals Korea is to be notified promptly by the physician.

Check the following at the end of the study or after the resolution of adverse event.

- Outcome: The evaluation of outcome will include: Record the date of recovery in case of ‘Recovered’ or ‘Recovered with sequelae’.
  - Recovered
  - Recovered with sequelae
  - Recovering
  - Not recovered
  - Unknown

- Causality of adverse event to the study drug: The causal relationship of adverse event to the study drug must be allocated by the physician according to the following criteria.

(1) Certain

- It follows a reasonable time sequence from administration of the drug (before and after the study medication).
- It could not be explained by other drugs, chemical substance or accompanying diseases.
- It has clinically reasonable reaction on cessation of the drug.
- It has pharmacological or phenomenological reaction to re-administration of the drug, where necessary.

(2) Probable/likely

- It follows a reasonable time sequence from administration of the drug (before and after the study medication).
- It could not be explained by other drugs, chemical substance or accompanying diseases.
- It has clinically reasonable reaction on cessation of the drug.

(No information on re-administration)

(3) Possible

- It follows a reasonable time sequence from administration of the drug.
- It could also be explained by other drugs, chemical substance or accompanying diseases.
- It lacks information or has unclear information on discontinuation of the drug.

(4) Unlikely

- It is not likely to have a reasonable causal relationship from administration of the drug. Rather, it seems to be temporary.
- It could also be reasonably explained by other drugs, chemical substances or latent diseases.

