\* Other causality of adverse event: If the adverse event is not related to the study drug, physicians should indicate the most appropriate cause from the followings and record in detail.

1. Disease under the study
2. Other disease (please specify)
3. Concomitant treatment drug or non-drug (please specify)
4. Others (please specify)

(5) Conditional/unclassified

- It needs more data to make an appropriate assessment or its additional data are being reviewed.

(6) Unaccessible/unclassifiable

- Lack of sufficient information or conflicting information hampers accurate causality assessment or supplementation or confirmation.

(7) Not applicable

- Action: Check relevant action.

- A. Discontinuation (Permanently, Temporarily or delayed)
- B. Dosage reduced
- C. Dosage increased
- D. No Change
- E. Unknown
- F. Not Applicable

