### **5.1.3. Causality assessment**

The investigator is required to assess and record the causal relationship. For all AEs, sufficient information should be obtained by the investigator to determine the causality of each adverse event. For AEs with a causal relationship to Inlyta, follow-up by the investigator is required until the event and/or its sequelae resolve or stabilize at a level acceptable to the investigator, and Pfizer concurs with that assessment.

An investigator's causality assessment is the determination of whether there exists a reasonable possibility that Inlyta caused or contributed to an adverse event. If the investigator's final determination of causality is "unknown" and s/he cannot determine whether Inlyta caused the event, the safety event must be reported within 24 hours.

If the investigator cannot determine the etiology of the event but s/he determines that Inlyta did not cause the event, this should be clearly documented on the case report form and the NIS AEM Report Form.

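### SAP 6.2 counts adverse events coded 'Not applicable', a code neither document defines, as related to INLYTA, which may inflate adverse drug reaction incidence

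*SAP*

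**What the plan says.** - SAP 6.2, item 2, opens the related group with "Related to INLYTA®: ① Certain". It continues with codes 2, 3, 5 and 6 and ends with "⑦ Not applicable".
- The other group has one member: "Not related to INLYTA®: ④ Unlikely".
- The SAP restricts the summary by other causality (Table 21) to events classed as not related, which under this split means 'Unlikely' only.
- Protocol 3.5.4.9.1 uses the same seven codes. Codes 1 to 6 each have a description; the last is the bare label "7) Not applicable".
- Code 4 is described by "It is not likely to have a reasonable causal relationship from administration of the drug". Between codes 4 and 5 the protocol adds: "If the adverse event is not related to the study drug, physicians should indicate the most appropriate cause from the followings and record in detail".
- Code 5 is for events that need more data or are under review. Code 6 is for cases where "Lack of sufficient information or conflicting information hampers accurate causality assessment or supplementation or confirmation".
- SAP 6.2, item 1, asks for the incidence of ADRs, serious ADRs, unexpected ADRs and unexpected serious ADRs with 95% confidence intervals. The SAP gives no separate definition of an ADR.

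**The concern.** Counting codes 5 and 6 as related is a defensible cautious rule: causality is unresolved, so the drug is not excused. That reasoning does not clearly extend to code 7. Unresolved cases already have two codes, and nothing in either document indicates that a physician who ticks 'Not applicable' suspects the drug.

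Some recorded events could plausibly attract that label. A malignancy with a fatal outcome must be entered as a Grade 5 serious AE (Protocol 3.5.4.9.1 and 5.2.2), and lack of efficacy is listed among examples of AEs (Protocol 5.2.1). If a death from progression were coded 7, SAP 6.2 would count it as a serious ADR and omit it from Table 21 even if the physician had recorded the disease as the cause.

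ADR incidence is a main safety output of a study set up to monitor AEs in practice. Part of it would rest on a code whose meaning is left to each site.

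**Working it through.** The plan states no figure to reproduce: the minimum of 100 subjects is a regulatory number, and neither an ADR rate nor a frequency of code 7 is given. The check compares the passages, traces the affected outputs, and then illustrates the size under stated assumptions.

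**Step 1: mapping**

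| Code | Protocol description | SAP 6.2 group |
|---|---|---|
| 1–3 Certain, Probable/likely, Possible | Yes | Related |
| 4 Unlikely | Yes | Not related |
| 5 Conditional/unclassified | Yes: more data needed or under review | Related |
| 6 Unaccessible/unclassifiable | Yes: insufficient or conflicting information | Related |
| 7 Not applicable | None | Related |

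Moving code 7 into the related group can only add events and subjects to the ADR numerators. The direction is therefore certain; the size is not.

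**Step 2: outputs affected**

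- All-ADR incidence per subject: Tables 8 and 15, and the special-population Tables 32–35. Table 20 separates the codes but counts events, so subjects cannot be rebuilt from it. Table 19 is binary.
- Serious and unexpected ADR incidence: Tables 8, 9, 11 and 13. Tables 10, 12 and 14 list serious, unexpected serious and unexpected AEs by subject with causality, so these rates can be recomputed without code 7. Those listings are marked for the re-examination report only, so periodic reports offer no such route.
- Table 21: code-7 events are left out.
- Tables 23–25 analyse all AEs regardless of causality and are unaffected.

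**Step 3: size per subject**

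Let N be the subjects analysed and k the subjects whose only 'related' event is coded 7. The rise in ADR incidence is k/N. With N = 100, each such subject adds 1/100 = 1 percentage point. The table shows incidence with exact (Clopper–Pearson) 95% intervals. The base rates, the values of k and the interval method are assumptions; the SAP names no interval method.

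| Base without code 7 | k = 0 | k = 2 | k = 5 | k = 10 |
|---|---|---|---|---|
| 30% | 30% (21.2–40.0) | 32% (23.0–42.1) | 35% (25.7–45.2) | 40% (30.3–50.3) |
| 50% | 50% (39.8–60.2) | 52% (41.8–62.1) | 55% (44.7–65.0) | 60% (49.7–69.7) |
| 70% | 70% (60.0–78.8) | 72% (62.1–80.5) | 75% (65.3–83.1) | 80% (70.8–87.3) |

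**Step 4: size by share of events**

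Assume AEs per subject are Poisson with mean λ and a share r of AEs is classed as related, independently. ADR incidence is then 1 − exp(−λr). Let code 7 be a share s of AEs, moving r to r + s. Codes 1–3 are assumed to make up 40% of AEs, and codes 5–6 either 0% or 10%.

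| λ | r without code 7 | Incidence, s = 0 | s = 5% | s = 20% | Rise (points) |
|---|---|---|---|---|---|
| 2 | 0.40 | 1 − exp(−0.8) = 55.1% | 59.3% | 69.9% | 4.3 to 14.8 |
| 2 | 0.50 | 1 − exp(−1.0) = 63.2% | 66.7% | 75.3% | 3.5 to 12.1 |
| 4 | 0.40 | 1 − exp(−1.6) = 79.8% | 83.5% | 90.9% | 3.7 to 11.1 |
| 4 | 0.50 | 1 − exp(−2.0) = 86.5% | 88.9% | 93.9% | 2.5 to 7.5 |

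The rows with r = 0.50 suit the proposed fix better, because it keeps codes 5 and 6 as related. Any use of those codes shrinks the increment from code 7.

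**The case against.** The strongest reply is that the protocol already tells physicians where a not-related event belongs. The instruction to record another cause comes straight after the criteria for 'Unlikely' and before code 5, and the SAP's not-related group matches it. Nothing sends such events to code 7. This stands: a reader might infer that the scale leaves a physician who is sure the drug played no part with two equal choices, and the documents do not support that. Misclassification is a risk created by an undefined label, not a consequence of the design.

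A reader might also infer that the grouping contradicts Protocol 5.1.3, which says that if "s/he determines that Inlyta did not cause the event, this should be clearly documented on the case report form". That is a duty to record, it applies where the etiology cannot be determined, and 'Unlikely' together with the other-cause field satisfies it. It sets no rule for grouping codes in analysis.

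Third, the listings recover much of what the summary tables hide. This also stands for serious and unexpected ADRs in the re-examination report. It does not cover all-ADR incidence, the special-population tables or the periodic reports.

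Finally, Protocol 3.12 says the SAP follows the regulator's post-marketing guideline, so the grouping may not be the sponsor's to change. The documents cannot settle this, and the fix allows for it.

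**Conclusion.** The point holds as a cheap improvement. SAP 6.2 assigns an undefined code to the related group and so may inflate subject-level ADR incidence in Tables 8, 15 and 32–35, and the serious and unexpected ADR rows in periodic reports. It also removes code-7 events from Table 21. In the re-examination report the serious and unexpected rates can be regrouped; the all-ADR rate cannot.

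The size is one percentage point per affected subject at N = 100, and zero if code 7 is unused. The larger rises in the working depend on assumed use of code 7 at 5–20% of AEs, which has no basis in the documents. It would be wrong to conclude from them that inflation has been shown.

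The conclusion also assumes that ADR means an AE in the SAP's related group. This is inferred, since the related/not-related split is the only rule the SAP provides.

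**What to change.** 1. Define code 7 on the CRF and query every code-7 entry before database lock.
2. State in the SAP which causality codes make an event an ADR.
3. Show remaining code-7 events as a separate line in Table 19, and include them in Table 21 where another cause is recorded.
4. Add to Table 8 one ADR row that excludes code 7 only, keeping codes 5 and 6 as related so that the row isolates the effect of this code. A further row restricted to certain, probable and possible is optional.
5. If the regulator's format fixes the broad grouping, keep it as the main row and present these as sensitivity rows.

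The cost is a CRF definition, the queries, some SAP wording and one or two table rows. The downside is that a possibly lower ADR figure appears beside the cautious one; because both are shown, no event is hidden.
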